TITLE: Evaluation of Abdominal Wall Block with Liposomal Bupivacaine for Post-Operative Analgesia in Donor Nephrectomy

NCT#: NCT03294109

DATE: May 20, 2020

Study Title:

“Evaluation of Abdominal Wall Block with Liposomal Bupivacaine for Post-Operative Analgesia in Donor Nephrectomy”

List of Abbreviations:

TAP block: Transverse abdominis plane block

TQL block: Transmuscular quadratus lumborum block

LA: Local Anesthetic

Principal Investigator, Research Team, and Study Site:

Principal investigators: [name] MD, [name] MD

Co-Investigators: [name] MD, [name] MD, [name] MD, [name] MD, [name], [name], [name]

Research team and contact information:

UCLA Department of Anesthesiology
and Perioperative Medicine

Ronald Reagan UCLA Medical Center

[name]

[name]

[contact]

University of California, Los Angeles

Department of Urology

David Geffen School of Medicine at UCLA

[name]

[name]

[name]

[contact]

Study site: UCLA Medical Center, Ronald Reagan Hospital

Background and study population

The study population will include patients greater than 18 years of age undergoing laparoscopic donor nephrectomy surgery.

Study Design

Randomized blinded controlled clinical trial

Sample Size

50 each arm. 100 total.

Study Duration

18-24 months.

Primary Objective

To determine the degree of pain control in patients receiving a long acting TQL block in addition to a short half-life TAP block compared to TAP block alone (i.e., the current standard of care) after laparoscopic donor nephrectomy. This outcome will be measured using pain scores on a numeric scale obtained during standard inpatient care as well as via the APS-POQR and PROMIS-29, two standard, validated questionnaires.

Secondary Objectives

- To determine patient satisfaction as measured by a satisfaction item at post-operative days 1 and 90.
- To measure changes in quality of life via the PROMIS-29, bowel function via the Bowel Habits Questionnaire (BHQ), male (International Index of Sexual Function; IISF) and female sexual function (Female Sexual Function Index; FSFI) across time and in the study group (patients receiving liposomal bupivacaine TQL block in addition to TAP block) as compared to our conventional post-operative pain management. See attached questionnaire schedule for timing of these items.

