Secondary objectives include patient satisfaction scores obtained with a validated satisfaction survey administered to each patient prior to discharge; nausea and vomiting requiring medical intervention; block-related complications noted in the immediate perioperative period or post-operative period; and total opiate requirement during the hospital stay and for 90 days after surgery. We will also monitor the return of bowel function, sexual function and general health using standardized quality of life instruments. Sexual function following kidney donation has not been closely evaluated; yet many patients ask about the potential impact of surgery on this bodily function that is important to a normal quality of life. Each patient will complete the validated survey instruments prior to and after kidney donation. Patients are not required to answer any questions. We will evaluate attitudes toward living kidney donation in relationship to pain control.

Study design/methodology:

This is a randomized, single-blinded controlled trial in patients greater than 18 years of age who have agreed to proceed with laparoscopic donor nephrectomy. Patients meeting these criteria will be offered participation in the study. They will be advised of the risks and potential benefits of the study. They will be advised of the request to answer surveys and have information regarding their care collected for research. They will be advised that participation requires the ability to answer questions using electronic communications. Participation is optional and standard anesthesia and pain control will be provided to all patients. Patients have the option to withdraw

from the study at any time and are not required to answer any of the survey questions. Enrolled patients will not know which treatment is provided.

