Those patients who agree to participate and provide written consent will be enrolled into the study and instructed in the electronic completion of study questionnaires using the Urology Patient Data Waystation (UPDW). Unique, personalized log-in information will be sent to the patient either by email or using the secure MyChart messaging system, based on patient preference, to access UPDW for each time point. Initial questionnaires at enrollment will collect baseline quality of life, bowel and sexual function, and demographic data. When the surgery date has been determined, patients will receive a message to complete a second set of baseline survey questionnaires using the same system if their surgery date is more than 6 months past the date of completion of their initial baseline survey. Those participants who completed their initial baseline within 6 months of their surgery date will only complete one baseline survey.

When surgery is scheduled, each enrolled patient will be randomized (alternating, blocked randomization) to either the study group to receive liposomal bupivacaine TQL block in addition to standard of care post-operative pain management or to the control group to receive our current standard of care. Randomization will maintain equal numbers of participants in each group by sex due to the increased risk of post anesthesia nausea in females.

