The following study variables will be collected postoperatively following arrival in the post-anesthesia care unit: Current and maximum intensity pain scores will be documented by nurses in the electronic medical record (EMR). Total opiate dose consumed every 24 hours will be collected from EMR and electronic survey after discharge. Patient satisfaction will be evaluated using the Revised American Pain Society Patient Outcome Questionnaire (APS-POQ-R) provided on post-operative day 1 by a research assistant or study coordinator. The incidence of nausea or vomiting will be extracted from nursing notes and queried via electronic surveys. Post-discharge, which is typically 1-2 days following surgery, patients will be sent surveys delivered by the UPDW database server 3, 5, 10, 30, and 90 days post-surgery. If patients do not respond 90 days post-surgery study team will contact patients to attempt to have the exit survey completed.

Complications will be documented in the EMR by the anesthesia pain service, urology service, and nurses who will monitor these patients while admitted. Urology and study staff will follow the patients following discharge, including a post-operative office follow-up approximately 1 week post-surgery, as is standard of care

Study Population:

Patients at least 18 years of age undergoing laparoscopic donor nephrectomy. Pregnant patients will be excluded. Patients with local infection at the potential block site or any contraindication to kidney donation, local, or general anesthesia will be excluded.

Study Duration/Study Timeline:

We anticipate a high level of enrollment since most patients have previously consented to having a block placed and pain minimization is generally a high priority. Given the current volume of donor nephrectomies we expect enrollment to be complete within one year. The duration of the study will depend on the timing from consent for surgery until the operation is scheduled. In most cases this occurs within 2-3 months. The study data collections will conclude 90 days after surgery unless the patient was not able to complete the survey. Additional attempt to contact the patient after 90 days post-surgery may be enacted to have the patient(s) complete an exit survey. See the attached study time line in Appendix A.

Statistical Analysis Plan:

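### The only allocation rule, alternating blocked randomization, permits a deterministic sequence in a trial labelled randomized, and no concealment of upcoming assignments is described

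*Combined protocol and SAP*

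**What the plan says.** The Study Design entry reads "Randomized blinded controlled clinical trial", and Study design/methodology repeats the label: "This is a randomized, single-blinded controlled trial in patients greater than 18 years of age".

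The method appears once, later in Study design/methodology. Once surgery is scheduled, "each enrolled patient will be randomized (alternating, blocked randomization) to either the study group" or to the control group. The same paragraph adds: "Randomization will maintain equal numbers of participants in each group by sex". The reason given is the higher risk of nausea in women. No block size is stated.

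Consent and enrolment come first: "Those patients who agree to participate and provide written consent will be enrolled into the study". Study Duration/Study Timeline describes the interval from consent for surgery to scheduling: "In most cases this occurs within 2-3 months". Under Informed Consent Process, the donor nephrectomy surgeon identifies patients, introduces the study and completes consent, and the study coordinator enrols those who consent by mail.

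No section says how the sequence is generated, who prepares, holds or releases it, or how upcoming assignments are hidden. The only envelope mentioned is for returning mailed consent forms. Privacy and confidentiality deals with data and questionnaires. The skin-only needle insertion in controls and the wristband in both arms serve to keep patients blind after assignment.

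**The concern.** Alternation and blocked randomization are different rules. Under alternation each assignment is fixed by the one before it. Under blocked randomization the order within each block is drawn at random. Read literally, one sequence cannot be both. Two members of staff could each follow this sentence faithfully, and one of them would not be randomizing.

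Random, concealed allocation is what allows a difference between the arms to be attributed to the block. Here the TQL procedure visibly differs between arms for staff in the operating room, so past assignments can become known to them. If the sequence alternates, a past assignment gives away the next one. Anyone who has that knowledge and influence over surgery dates could, deliberately or not, affect who enters which arm. The planned comparison of pain scores is a t-test of means, which would not correct for that.

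**Working it through.** **What can be checked.** The plan gives no figure for allocation beyond 50 per arm and 100 in total (Sample Size), so there is none to reproduce. The question is how predictable the next assignment would be under each reading of the sentence.

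**1. Strict alternation, one list per sex.** Inputs: 100 patients (Sample Size) and two lists (assumed from the balance-by-sex sentence). Only the first assignment in each list is open, and every later one follows from its predecessor: 100 − 2 = 98 of 100. This requires knowing one earlier assignment in each list and the scheduling order.

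**2. Strict alternation, one list for everyone.** This fixes 100 − 1 = 99 of 100. But one list would rarely balance the arms within each sex. Assuming 50 women and 50 men in random order, the chance of exactly 25 women in each arm is C(50,25) × C(50,25) / C(100,50) = 0.158, about 16%. Two lists fit the balance requirement better, so 98 is the figure to use on the alternation reading.

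**3. Random permuted blocks, for comparison.** The block size is not given; take 4 as an illustration, with an observer who knows the size and every earlier same-sex assignment. The six equally likely orders are AABB, ABAB, ABBA and their mirror images.
- Certain assignments: two in AABB and one each in ABAB and ABBA, so on average (2 + 1 + 1)/3 = 1.33 of 4, or 33%.
- Correct best guesses by position: 1/2, 2/3, 2/3, 1. The sum is 2.83 of 4, or 71%.
- If the last three same-sex assignments are unseen, the figure falls to 50%, which is chance.

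The two readings of one sentence therefore differ widely: 98% of assignments fixed, against 33% even for a fully informed observer of blocks of 4.

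**4. Prediction at recruitment, if alternation is strict.** Could a recruiter guess the arm from the order of consent? Inputs: enrolment expected within one year (Study Duration/Study Timeline), so 100/52/2 = 0.96 consents per week per sex (equal split and random arrivals assumed); 50 patients per sex; scheduling within 2-3 months of consent. The guess is odd or even place in the consent order, and 4,000 strata were simulated.

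| Interval from consent to scheduling (assumed uniform) | Correct guesses |
|---|---|
| 0 to 3 months | about 50% |
| 0 to 2 months | about 51% |
| 2 to 3 months | about 54% |

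The first two rows follow the natural sense of *within*. The third takes two months as a minimum, which the text does not say. All three are at or near chance. The stated interval starts at consent for surgery, which precedes study consent, so it only approximates the interval of interest.

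**5. Where that leaves the exposure.** A patient's place in the order is settled when surgery is scheduled. That is when allocation occurs, and the documents do not say who sets the dates or whether past assignments reach that person.

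**The case against.** The strongest reply is that the paragraph speaks of randomization three times and of alternating only once. The word might mean no more than that blocks keep the arms level, or that the two sex lists are handled in turn. The method used may have been sound. This stands in part: the text is ambiguous, and deterministic allocation is not established. But no section supports the looser reading, and an allocation rule should not depend on the reader choosing the sound one.

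A second reply is that silence is not evidence of exposure. That also stands, to this extent: the documents show that no safeguard is described, not that none existed.

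Two stronger readings are tempting, and the documents support neither.
- *Recruitment could be steered.* A reader might infer that the surgeon, who introduces the study, could foresee the arm. Enrolment precedes allocation, and over the stated interval the consent order predicts the arm at about chance. Much better prediction would need nearly constant intervals, and no section indicates that.
- *Selective withdrawal could unbalance the arms.* The protocol says "Patients have the option to withdraw" at any time. But that is the patient's choice, patients are not told their treatment, and no section describes staff withdrawing patients. The remark in the Statistical Analysis Plan that some may not complete the study covers any non-completion, including missed surveys.

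**Conclusion.** The point holds as a defect in the allocation rule as written: it permits a deterministic sequence in a trial labelled randomized, and it describes no concealment. On the strict reading, with one list per sex, 98 of 100 assignments are fixed by the scheduling order and one earlier assignment per list. On a permuted-block reading, predictability is far lower. The 98 rests on that strict reading and on someone knowing past assignments; it measures predictability, not bias.

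The main risk lies in the order of scheduling. A reader might go further and infer that the trial was not randomized or that its result is biased. The documents support neither inference, and the size of any bias cannot be derived from them. The sample size is unaffected.

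**What to change.** In the allocation paragraph of Study design/methodology:
- Delete *alternating*.
- Specify a computer-generated permuted-block list stratified by sex, with block sizes not disclosed to recruiting, scheduling or surgical staff.
- Name a role outside recruitment and scheduling that prepares and holds the list.
- State that each assignment is released only after the patient is enrolled and the surgery date is fixed, and by what means (for example, sealed opaque envelopes or a locked electronic module).

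If patients have already been allocated, record and report the method actually used, and call the design quasi-randomized if it was alternation.

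The cost is one short amendment, one generated list and the handling of a concealed list. Stratification by sex and enrolment before allocation are already in the plan. Sample size, treatment and data collection do not change.

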- To determine if patient-reported nausea and vomiting at post-operative days 1, 3, 5, 10, and 30 is significantly decreased in patients in the study group.
- To measure the rate of block-related complications in the study group. Potential complications include local anesthetic toxicity, intravascular injection, persistent weakness or paresthesia, nerve injury, voiding dysfunction, persistent numbness, altered sexual function, bleeding/hematoma, hypotension, infection at the injection site, or other complaints related to the block.
- To determine if narcotic requirements postoperatively are lower in the study group. To determine total anesthetic and operative time, as well as costs.

Background and Significance:

Living kidney donors are carefully screened prior to recommending kidney donation. They are informed of the risks of surgery and the option of changing their mind until the day of kidney donation. All of the patients have an abdominal and pelvic CT scan to evaluate the renal anatomy and to screen for abnormalities. Our goal is to make the operation as minimally invasive as possible and to facilitate the return to normal function as quickly as possible. Currently, most patients need narcotics to control the pain after surgery. These medications can have significant side effects including nausea and constipation, which can delay recovery from the operation.

Since the first successful living donor kidney transplant between identical twins, the special nature of this operation and the anesthetic management has been debated (1). Extensive efforts have been made to improve the safety and reduce the morbidity of kidney donation. At UCLA, laparoscopic kidney donation was introduced in 1999, and is now the standard of care for approximately 150 of these operations annually. Ketorolac analgesia was added to reduce pain in 2002 and the procedure has continued to evolve to promote return to normal function as soon as possible (2). The median length of stay for these patients is currently 1.4 days.

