A review of the literature identified three publications with enhanced recovery from surgery (ERAS) protocols. The Univ. of Michigan protocol uses a transversus abdominus plane (TAP) block under ultrasound guidance using a hydrodissection technique with normal saline followed by 15 to 20 mL of 0.5% ropivacaine per side with length of stay (LOS) of 1 day after surgery (3). The Duke protocol uses a liposomal bupivacaine TAP block and a hand assisted approach, which also achieved a one day LOS (4). A randomized study of hand assisted laparoscopic kidney donation at the Univ. of Minnesota compared bupivacaine to liposomal bupivacaine for subcostal TAP block which showed a significant reduction in pain scores for the liposomal bupivacaine 24-48 hours after surgery, but a LOS of 2-3 days in both groups (5).

An alternative local anesthetic approach in laparoscopic gynecologic operations and pediatric pyeloplasty is the transmuscular quadratus lumborum (TQL) block. The most important advantage of TQL block over TAP block is a consistent posterior spread of local anesthetic up to the paravertebral space (6). In preliminary studies, we have placed a TQL block in 6 patients using bupivacaine and methylene blue. These patients had excellent pain relief for approximately 12 – 18 hours, but then had more need for outpatient narcotics after the local anesthetic effect wore off. In patients with bupivacaine TAP block, placed either by ultrasound, or by direct visualization with the laparoscope, pain relief is achieved for the anterior abdominal wall, but patients still need narcotics for relief of pain toward the back. Complications that have been reported with TQL block include hypotension which may have been due to sympathetic blockade, and motor dysfunction of the leg for over 24 hours (7,8). Based on our minimal experience with TQL block and review of the literature, it is our hypothesis that the optimal pain management for fully laparoscopic donor nephrectomy is a combined TQL block placed after the induction of anesthesia and a TAP block placed after the midline incision is closed using a long acting local anesthetic.

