Liposomal bupivacaine is a novel local anesthetic designed for prolonged pain relief, up to 72 hours. Despite its long-acting analgesic potential, liposomal bupivacaine is significantly more expensive than other local anesthetic alternatives. The primary aim of this investigation is to examine whether or not liposomal bupivacaine provides superior pain relief, clinically significant

opioid-sparing effects, and improved patient satisfaction versus a control group with our current local anesthetic to justify its cost.

Objectives:

The primary objective of the study will be to determine the degree of improvement in pain control seen in patients receiving a TQL block in addition to our conventional method of TAP block compared to TAP block alone and intravenous/PO opioids based management. Both groups will have injection of 20 cc 0.25% bupivacaine in the transverse abdominus plane and subcutaneous infiltration of 10 cc around incisions. This is already our standard of care protocol. In addition to this standard care, the study group will receive a TQL block of 20 cc of liposomal bupivacaine mixed with 10 cc of normal saline will be under ultrasound guidance following induction of general anesthesia.

Both groups will have the same bowel preparation, ERAS fluid management, access to antiemetic, opioids, acetaminophen, and NSAIDs on a PRN basis. Assessments of pain scores will utilize the visual analog scale (VAS) evaluated by nursing staff when obtained with the vital signs per PACU and floor nursing protocol. Information regarding use of opioids after discharge will be collected with a pain diary and electronic surveys at least till 90 days. If a patient does not complete their 90 day survey the study team will contact them again to attempt an exit survey.

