If returning to the clinic for an additional consent visit would be too burdensome for the patient – many eligible patients drive or fly several hours to attend appointments at UCLA – the study coordinator will arrange for the patient to complete consent by mail. To do so, the study coordinator will give the patient two copies of the consent form, the HIPAA form, the patient bill of rights, and a pre-paid envelope for returning signed documents. The envelope will be addressed to [name] and delivered to his locked office. The study coordinator will follow up with the patient within approximately 2 weeks to determine whether the patient has made a decision on whether to participate and again probe for further questions, which will be answered by the study coordinator or forwarded to a study surgeon depending on the content. Once the patient has made a decision, the study coordinator will schedule an appointment for the patient to speak with a study surgeon to confirm all questions have been answered and to complete the consent process. The patient may then place the signed consent and HIPAA forms in the pre-paid envelope to mail to the study team. Once the forms are received, the study coordinator will enroll the patient and send the baseline survey as usual. Regardless of methodology, the consent

process will be documented, including date and time of consent, via paper forms which will be stored with the consent form and signed by the physician obtaining consent.

Patients will be recruited until our goal sample size of 50 patients in each arm of the study is achieved. At that time statistical analysis will be performed. Any major complications will be reviewed to determine if the study should be continued.

Privacy and confidentiality:

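### After discharge the plan names no item, assessment time or data source for weakness, numbness, voiding or injection-site complications, so these may be under-reported

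*Combined protocol and SAP*

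**What the plan says.** The Secondary Objectives set out to measure the rate of block-related complications in the study group. The list of candidates includes "persistent weakness or paresthesia, nerve injury, voiding dysfunction, persistent numbness", as well as altered sexual function and infection where the needle went in. The Objectives section counts complications in the perioperative or post-operative period and gives no end date.

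The recording method is in Study design/methodology: "Complications will be documented in the EMR by the anesthesia pain service, urology service, and nurses who will monitor these patients while admitted". The next sentence adds: "Urology and study staff will follow the patients following discharge, including a post-operative office follow-up approximately 1 week post-surgery". Data Safety Monitoring plans intermittent analysis of adverse outcomes for at least 90 days and does not say which data it will use.

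Three statements in Background and Significance bear on timing:

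- On stay: "The median length of stay for these patients is currently 1.4 days".
- On the drug: it is "designed for prolonged pain relief, up to 72 hours".
- On reported complications of the TQL block: they include "motor dysfunction of the leg for over 24 hours".

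Surveys go to patients through UPDW on days 3, 5, 10, 30 and 90, and day-90 non-responders are contacted for an exit survey.

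**The concern.** Several listed complications are defined by lasting. Weakness or numbness can be called persistent only once the block should have worn off, and at a typical discharge it may still be active. The inpatient record therefore cannot measure these events, and their rate depends on what is collected afterwards.

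For that period the text describes follow-up in general terms only. It names no question, examination or fixed time directed at weakness, numbness, voiding or the injection site. If such events reach the record only when a patient raises them or a clinician happens to note them, the reported rate could be low because nobody asked. This matters in healthy donors, and in a trial where leg weakness after this block is a risk that the protocol itself cites.

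**Working it through.** The plan gives no figure for this point to reproduce. The check is one of timing and of how outcomes are matched to sources.

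**Timing.** Inputs: median stay 1.4 days and drug effect up to 72 h (Background and Significance); discharge typically at 1–2 days, visit at about 1 week, surveys on days 3 to 90 (Study design/methodology). Stay is assumed to be counted from surgery.

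- Median discharge: 1.4 × 24 = 33.6 h. The 1–2 day range is 24–48 h. All of these fall before 72 h.
- Day 3 survey: 3 × 24 = 72 h, at the limit of the stated effect.
- Day 5 survey: 5 × 24 = 120 h, which is 48 h past the limit.
- Office visit: 7 × 24 = 168 h, which is 168 − 72 = 96 h past the limit.
- Day 10 survey: 10 × 24 = 240 h, which is 240 − 72 = 168 h past the limit.

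The contacts at which persistence could be judged therefore exist. The question is whether any of them is assigned to it.

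**Outcome against stated source.**

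| Outcome | In hospital | After discharge |
|---|---|---|
| Opioid use | EMR | Electronic survey; pain diary |
| Nausea or vomiting | Nursing notes | Electronic survey |
| Sexual function | – | Named questionnaires for men and women |
| Weakness, numbness, voiding, injection site | EMR | General follow-up including the 1-week visit; no item or content stated |

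Where the protocol intends a survey to carry an outcome, it says so. For the last row it does not.

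**What under-recording could do.** The event rates and the capture fraction below are assumptions, because the documents give neither. With n = 50 treated patients, true rate p and capture fraction c, the chance of recording at least one event is 1 − (1 − pc)^50.

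| Assumed p | Full capture (c = 1) | Half capture (c = 0.5) |
|---|---|---|
| 2% | 1 − 0.98^50 = 64% | 1 − 0.99^50 = 39% |
| 5% | 1 − 0.95^50 = 92% | 1 − 0.975^50 = 72% |

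If no event is recorded in 50, the one-sided 95% upper bound is 1 − 0.05^(1/50) = 5.8%. That bound applies to the true rate only if capture is complete. At half capture it becomes 5.8% / 0.5 = 11.6%.

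**The case against.** A reader might infer that persistent deficits will be missed. The documents do not support that. The 1-week visit comes about 96 h after the stated limit of drug effect, so a lasting deficit could be seen there. The sentence on follow-up introduces that visit with a word meaning that other contacts are possible. Patients have access to transplant and urology staff, and adverse outcomes are to be analysed for at least 90 days. All of this stands.

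A reader might also take the hours between a median discharge and 72 h as a measure of what is lost. They are not: in that window the drug may still be acting, so no deficit can yet be called persistent. The 72 h is also an upper limit for pain relief, not a fixed duration of every block effect.

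Nor can it be said that the surveys omit these symptoms. The attached questionnaire schedule and Appendix A are not in the text available, and no questionnaire item is reproduced. What can be said is that the text does not describe such items.

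Finally, this is one secondary objective, no test is planned for it, and 50 treated patients cannot exclude uncommon harms even with perfect recording. That is fair and limits the weight of the point. It does not answer why complications lack the survey route that opioids and nausea have.

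**Conclusion.** The point holds in a limited form. The plan follows patients long enough to detect persistent weakness or numbness, but the available text assigns no item, time or data source to these events after discharge, nor to voiding or injection-site problems. They may therefore be under-reported, by an amount that the documents do not allow anyone to estimate. The 64% to 39% and 92% to 72% contrasts show only the possible scale, under assumed rates of 2% and 5% and an illustrative half capture.

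No sample size or other planned figure changes. The conclusion rests on the text as supplied; if the questionnaire schedule already contains such items, what remains is to cite them as the source and define persistence. The change is worth making because it is cheap and improves on passive recording.

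**What to change.** 1. Add a few identical yes/no items to the existing UPDW surveys on days 3, 5, 10, 30 and 90 in both arms: leg weakness, numbness or tingling, difficulty voiding, and a problem at the injection site. If the attached questionnaire schedule already has them, cite it.
2. State in advance the survey time at which weakness or numbness counts as persistent. It should lie after the 72-hour effect; day 10 is one example.
3. Name the surveys together with the EMR as the source for the complication rate, and report it by arm. Because patients are not told their arm, the same questions in both give a patient-blinded comparison.

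The cost is slightly longer surveys, a wording change, and some nonspecific positive answers, which the control arm puts in context. No extra visits or assessors are needed.
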